6.2 General Concomitant Medication and Supportive Care Guidelines

All concomitant medications and medication history for 2 weeks MUST be recorded in the eCRF, and include: drug name, dose, frequency of administration, start and stop dates, and indication. All prior medications used to treat CMML will be recorded regardless of when they were received by the subject. Information collected for these medications will include dates of use, best treatment response (e.g., disease improvement, stabilization of disease or no improvement/disease progression), and reasons for stopping therapy. Any change in dosage of any concomitant medication (change in dose or frequency) MUST be recorded in the eCRF, to include: drug name, dose, frequency of administration, start and stop dates and indication.

6.3 Permitted Medications

6.3.1.1 Growth Factors

Erythropoiesis-stimulating agents (ESAs) are allowed for anemia during the study as per accepted standards in the treatment of CMML as long as the ESA was initiated >8 weeks prior to the first dose of ruxolitinib. Patients who enter the study on ESAs should continue at the same dose schedule until the optimal dose of study medication has been established. G-CSF is allowed during the study for patients with severe neutropenia and recurrent infections. Patients who enter the study on G-CSF should continue at the same dose schedule until the optimal dose of study medication has been established. GM-CSF is not permitted at any time during the study as preclinical evidence suggests that GM-CSF may be important for CMML proliferation and survival.

6.3.1.2 Systemic corticosteroids

Systemic corticosteroid doses greater than the equivalent of 10 mg prednisolone per day is not permitted, unless use is part of an ruxolitinib-dose tapering strategy. (see section 7 Optional Dose Tapering Strategy).

6.3.1.3 Aspirin

Aspirin in doses exceeding 162 mg per day is not permitted. Low dose aspirin (≤ 162 mg/day) and non-steroidal anti-inflammatory agents (acetaminophen, Ibuprofen) may be used.

6.3.1.4 Medications that are inhibitors of CYP3A4

When concomitant administration of a potent systemic inhibitor of CYP3A4 metabolizing enzymes (ketoconazole, clarithromycin, itraconazole, nefazodone and telithromycin, see section 7) that is required for subject management, the dose of ruxolitinib tablets must be adjusted as described in section 7. Based on the low overall bioavailability of topical ketoconazole, with very low systemic levels seen following topical administration, no dose adjustment of ruxolitinib is needed for use with topical ketoconazole.

6.3.1.5 Blood Products

The use of blood products to include packed red blood cells (PRBCs) and platelet transfusions are permitted and to be given at the discretion of the treating physician. Recommended guidelines for transfusion include a platelet threshold of 10,000/L for platelet transfusion and a hemoglobin threshold of 8g/dL for PRBC transfusion.

6.4 **Prohibited Medications**

Patients must abstain from using prohibited prescription or non-prescription drugs within 7 days or 5 half-lives (whichever is longer) prior to the first dose of study medication and until completion of follow-up procedures (Exclusion Criteria).

The following medications are prohibited during the study:

- Any prior or concomitant use of another JAK inhibitor.
- Any investigational medication other than the study drugs.
- Use of the potent inducers of CYP3A4, rifampin and St John's Wart, is not permitted at any time during participation in the study.
- The GM-CSF growth factor receptor agonists must not be used. Preclinical evidence suggests that it is important for CMML proliferation and survival and it is directly upstream for JAK2, the target of ruxolitinib. GM-CSF must not have been used for at least 28 days prior to receiving the first dose of study drug.

7 Duration of Therapy

Patients will be treated for a total of 16 weeks. For patients responding at week 16, treatment may continue until one of the following criteria applies:

- 7.1 Inter-current illness that prevents further administration of treatment,
- 7.2 Unacceptable adverse event(s),
- 7.3 Patient decides to withdraw from the study, or
- 7.4 General or specific changes in the patient's condition render the patient unacceptable for further treatment in the judgment of the investigator.
- 7.5 Evidence of disease progression by the IWG MDS/MPN criteria.

8 Duration of Follow-Up

Patients will be followed as per calendar on treatment for 17 weeks. After 17 weeks patient who continue on study will be followed monthly. Off study data on AML transformation and overall survival will be updated every 6 month or until death, whichever occurs first. Patients removed from study for unacceptable adverse events will be followed until resolution or stabilization of the adverse event.

9 Criteria for Removal from Study

9.1 Subject Completion

A subject will be considered to have completed the study if the subject meets at least 1 of the following criteria:

- 9.1.1 The subject has completed 16 weeks of treatment with study medication with no improvement.
- 9.1.2 The subject died during the study.
- 9.1.3 The subject experienced an AE that lead to withdrawal from the study.

9.2 Subject Withdrawal from Study

A subject may voluntarily withdraw from study medication or withdraw consent from the study at any time. The investigator may also, at his or her discretion, discontinue a subject from participating in the study at any time. The investigator will record the date and the reason for subject withdrawal from the study.

9.3 Subject Withdrawal from Study Medication

If the subject is permanently withdrawn from treatment with study medication, but does not withdraw consent, the investigator must make every effort to have the

subject complete all withdrawal assessments at the time of withdrawal, and complete all scheduled follow-up visits. Treatment with study medication must be discontinued if:

- The subject withdraws consent.
- Further participation would be injurious to the subject's health or well-being in the Investigator's medical judgment.
- The study is terminated.
- The subject becomes pregnant
- The patients exhibits leukemic transformation (as evidenced by bone marrow blast counts of at least 20%, or peripheral blast counts of at least 20% lasting at least 8 weeks.
- No clinical benefit has been attained after 16 weeks of treatment.
- Evidence of Disease progression according to IWG MDS/MPN criteria.
- a subject is significantly non-compliant with the requirements of the protocol.
- a subject has an adverse experience that would, in the investigator's judgment, make continued participation in the study an unacceptable risk.

Patients withdrawing from study can be tapered off of ruxolitinib over a 4 week period at the discretion of the investigator

10 DOSING DELAYS/MODIFICATIONS

All patients enrolled in the phase 2 portion may have the following dose delays/modifications once the MTD has been defined.

Ruxolitinib may be held by the Investigator at any time if there is concern about subject safety. Dosing must be halted immediately if either of the following occurs:

- Platelet counts fall below 10,000/ μ L and/or a life-threatening bleeding event
- Febrile neutropenia

Dosing may be reinstated following dose interruption using the re-start schema detailed in below.

10.1 Dose Adjustments:

In order to provide sufficient data to make the dose adjustment decisions, it is recommended that hematology parameters be obtained weekly and at least two times weekly for platelet count < 25,000/ μ L or ANC < 500/ μ L. In the event that any subject

permanently discontinues the study drug, regardless of reason, reasonable efforts should be made to have the subject return for an early termination visit. If the drug discontinuation is being contemplated for a reason other than low platelet count or low ANC, the use of a tapering strategy should be considered (see below). The date the subject discontinued the study drug and the specific reason for discontinuation will be recorded in the eCRF; eg, reasons such as discontinued due to inadequate efficacy or withdrawn due to adverse event. This information will be used to summarize the reasons for study discontinuation. Efforts will be made to follow patients who discontinue from the study in order to determine overall survival and leukemia free survival. Investigators will contact patients every 6 months to determine if patients have undergone leukemic transformation, or death, and for the latter, the cause of death.

10.2 Dose Adjustments in Ruxolitinib Tablets for Safety:

Dosing must be held if platelet counts decline below 10,000/ μ L or if a life-threatening bleed occurs with a platelet count below 20,000/ μ L. Doses must be decreased for platelet count values that decline greater than 50% of baseline **and** are **greater** than 25,000/ μ L to 75% of the defined MTD. Doses must be decreased for platelet count values that decline greater than 50% of baseline **and** are **below** 25,000/ μ L to 50% of the defined MTD. The dosing scheduled should be maintained at BID dosing to assure appropriate pharmacokinetics. Dose reductions should be executed by decreasing the individual dose and not the frequency of administration. In order to provide sufficient data to make the dose adjustment decisions, it is recommended that hematology parameters be obtained as defined in section 10.1. Dosing may be restarted or increased following recovery of platelet counts to acceptable levels. The following is the **recommended** dose restart/increase strategy:

In patients whom drug was held, ruxolitinib may be restarted at 50% of the MTD after platelet count has improved to pre-ruxolitinib baseline levels and/or febrile neutropenia has resolved for at least 2 weeks. In patients whom drug dose was decreased, ruxolitinib may be increased to the previous dose (MTD) after platelet count has improved to pre-ruxolitinib baseline levels and/or febrile neutropenia has resolved for at least 2 weeks. If criteria is met for discontinuation/dose modification

then ruxolitinib must be discontinued with no potential for restart. The objective for restarting or escalating after a reduction for safety is to find the highest safe dose of ruxolitinib for each subject, with increases in dose generally not more than in increments of 5 mg BID and not more often than every 2 weeks.

Dose Reductions for Concomitant CYP Inhibitor Usage

Ruxolitinib is metabolized in the liver by the cytochrome (CYP) P450 metabolizing enzyme system, predominantly by the 3A4 isozyme. With concomitant dosing of potent CYP3A4 inhibitors such as systemic ketoconazole (see Appendix B), plasma exposure of ruxolitinib increases approximately 2-fold. Thus, a dose reduction of ~50% for ruxolitinib is appropriate for patients who take systemic ketoconazole or other potent CYP3A4 inhibitors systemically as concomitant medication. BID doses will be decreased to the corresponding once daily dose as follows:

- If dose is 20 mg BID, change dose to 20 mg **QD**
- If dose is 15 mg BID, change dose to 15 mg **QD**
- If dose is 10 mg BID, change dose to 10 mg **QD**
- If dose is 5 mg BID, change dose to 5 mg **QD**
- If dose is 5 mg QD, no dose change is required.

Potent inhibitors of CYP3A4 include systemic ketoconazole, clarithromycin, itraconazole, nefazodone and telithromycin. NOTE: once the course of therapy using a CYP3A4 inhibitor has been completed, the subject should resume his/her prior BID dose regimen of study drug beginning the next day.

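### Sections 10 and 10.2 set different mandatory hold triggers for a life-threatening bleed, and the shared restart sentence has no condition on the bleed and is not tied to the reason for the hold

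*Combined protocol and SAP*

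**What the plan says.** **Section 10, opening text.** The general rule reads "Dosing must be halted immediately if either of the following occurs". The first trigger is a platelet count under 10,000/µL "and/or a life-threatening bleeding event"; the second is febrile neutropenia. No platelet limit is attached to the bleed. The section then sends all these interruptions to one restart rule: "Dosing may be reinstated following dose interruption using the re-start schema detailed in below".

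**Section 10.2.** The hold rule is stated again: "Dosing must be held if platelet counts decline below 10,000"/µL, or "if a life-threatening bleed occurs with a platelet count below 20,000"/µL. The restart strategy opens with "Dosing may be restarted or increased following recovery of platelet counts to acceptable levels" and is marked as recommended. A patient whose drug was held may restart at 50% of the MTD "after platelet count has improved to pre-ruxolitinib baseline levels and/or febrile neutropenia has resolved for at least 2 weeks". The same condition governs the return to the previous dose after a reduction.

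**Related text.** Section 4.2.1.1 excludes patients with platelets under 35,000/µL. Section 10 lets the investigator hold drug at any time on safety grounds. Section 9.3 makes discontinuation mandatory when the investigator judges that continuing would be injurious or an unacceptable risk. Section 10.3 gives hepatic impairment its own hold, recovery condition and second-occurrence rule.

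**The concern.** Both bleed rules are worded as obligations, both concern the same event, and they sit in the same chapter. If every life-threatening bleed requires a halt, the platelet qualifier in 10.2 does no work. If the qualifier is intended, the opening of Section 10 is too broad. The text does not show which was meant.

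The restart sentence adds a second gap. It serves every hold that Section 10 creates, yet it names only two recoveries, joins them with *and/or*, and does not say which one belongs to which hold. Restart criteria could then be met on paper while the event that caused the hold continues.

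What is at stake is patient safety in two serious events, and whether investigators, including those at external sites, can tell from the text what the protocol obliges them to do.

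**Working it through.** The plan gives no figure to reproduce here, so the check is a comparison of the rules.

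**Step 1: hold triggers**

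- Section 10: platelets < 10,000/µL, OR life-threatening bleed, OR febrile neutropenia.
- Section 10.2: platelets < 10,000/µL, OR (life-threatening bleed AND platelets < 20,000/µL).

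| Situation | Section 10 | Hold sentence in 10.2 |
|---|---|---|
| Platelets < 10,000/µL, with or without a bleed | halt | hold |
| Bleed, platelets 10,000 to < 20,000/µL | halt | hold |
| Bleed, platelets ≥ 20,000/µL | halt | no hold stated |

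The bleed triggers part at 20,000/µL. The lowest eligible entry count is 35,000/µL, which is 35,000 − 20,000 = 15,000/µL above that limit. A patient at the entry floor would have to lose more than 15,000/35,000 = 43% of the entry count before a bleed came under the 10.2 hold sentence. Every eligible entry count lies where the two rules differ.

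**Step 2: restart while the event that caused the hold is still present**

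The condition is "platelet count has improved to pre-ruxolitinib baseline levels and/or febrile neutropenia has resolved for at least 2 weeks". It is tested below under both readings of *and/or*. The *and* reading treats febrile neutropenia that never occurred in the same way as febrile neutropenia that has resolved.

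| Ongoing event that caused the hold | Platelets at baseline | Febrile neutropenia (FN) | *Or* reading | *And* reading |
|---|---|---|---|---|
| Bleed | yes | absent, or resolved ≥ 2 weeks | met | met |
| Bleed | yes | present, or resolved < 2 weeks | met | not met |
| FN | yes | ongoing | met | not met |
| FN | no | ongoing | not met | not met |
| Platelets < 10,000/µL | no | resolved ≥ 2 weeks | met, but blocked by the platelet-recovery lead-in | not met |

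In the first three rows platelets are at baseline, so the lead-in sentence on platelet recovery does not stop restart.

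**Step 3: a third reading**

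Suppose each half of the sentence belongs to its own hold reason. Low platelets and febrile neutropenia then each have a recovery condition, but a bleed has none. The missing bleed condition therefore survives all three readings. The febrile neutropenia gap exists only on the *or* reading.

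**The case against.** The strongest reply is that the hold rules overlap and do not collide. Every hold trigger in 10.2 is also a trigger in Section 10. At 20,000/µL or more, 10.2 is silent on a bleed; it does not direct dosing to continue. A site that applies the whole chapter halts under Section 10 and breaches nothing in 10.2. This stands, and it confines the harm to a site that works from 10.2 alone. It does not explain why 10.2 attaches a platelet limit to a bleed rule that Section 10 states without one.

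The safeguards are also real. Restart is permissive, recommended, and at 50% of the MTD. The investigator may hold at any time, and Section 9.3 obliges discontinuation for unacceptable risk. These lower the practical risk. None of them says which bleed trigger governs or supplies a recovery condition for a bleed.

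A reader might infer more than the documents support:

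- **That 10.2 means continued full dosing after a bleed at 20,000/µL or more.** It says no such thing, and it separately requires dose reductions when platelets fall by more than 50% from baseline.
- **That leaving febrile neutropenia out of the 10.2 hold sentence is a second conflict.** The 10.2 restart sentence names febrile neutropenia, so 10.2 presupposes the Section 10 hold.
- **That a patient held for both low platelets and febrile neutropenia may restart with platelets barely above the hold limit.** The lead-in makes restart follow platelet recovery. The acceptable level is undefined, but the requirement exists.
- **That the required delay before restart is zero days.** This takes the *or* reading alone and treats a count that never fell as having improved to baseline. The wording can equally presuppose an earlier fall.
- **That dose interruptions or adverse-event counts become non-comparable between sites.** This is a single-arm trial with no planned between-site comparison, and nothing in the documents shows such an effect.

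**Conclusion.** The concern holds in two parts.

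1. Sections 10 and 10.2 give different mandatory triggers for a life-threatening bleed. They differ at every platelet count of 20,000/µL or more. This follows directly from the text.
2. The restart sentence has no condition on the bleed under any reading and does not tie its conditions to the reason for the hold. That it could also be met during ongoing febrile neutropenia is a narrower finding. It assumes the *or* reading, platelets at baseline, and that a count which never fell counts as having improved to baseline.

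The entry floor describes counts at enrolment, not at the time of a bleed. The documents give no expected frequency of such bleeds in this population, so the number affected among the maximum of 29 patients cannot be estimated. The primary endpoint, the Simon boundaries and the analysis are untouched. This is an inconsistency in a safety rule, wrong as written, and the passages must be reconciled. No view is taken on which trigger or restart condition is right.

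**What to change.** - Reconcile the opening of Section 10 with Section 10.2. Keep one list of mandatory hold triggers covering bleeding, platelets and febrile neutropenia, and have the other section refer to it.
- Replace the shared *and/or* restart sentence with one line per hold reason, each giving the recovery condition for that reason, including bleeding.
- State how the conditions combine when a patient was held for more than one reason.
- Apply the same clarification where the sentence is repeated for return to the previous dose after a reduction, and define or remove the reference to acceptable platelet levels.

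The layout of Section 10.3 is a usable model, since it ties its hold and recovery to a single cause. The medical team chooses all thresholds and conditions. The cost is a wording amendment to Sections 10 and 10.2, with no added patients, visits or tests and no change to the statistical design.

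### Section 10.2 orders permanent discontinuation once dose-modification criteria are met, with no recurrence qualifier, so as written a first mandatory platelet dose reduction ends treatment and contradicts the restart rules around it

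*Combined protocol and SAP*

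**What the plan says.** Section 10 requires an immediate halt for platelets below 10,000/µL and/or a life-threatening bleed, and for febrile neutropenia. It then says "Dosing may be reinstated following dose interruption using the re-start schema" that follows.

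Section 10.2 requires a hold for platelets below 10,000/µL, or for a life-threatening bleed with platelets below 20,000/µL. It requires a reduction when platelets fall by more than 50% from baseline: to 75% of the MTD if the count is above 25,000/µL, and to 50% of the MTD if it is below.

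It then sets out what happens on recovery, under a strategy labelled as recommended:

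- General rule: "Dosing may be restarted or increased following recovery of platelet counts to acceptable levels".
- After a hold: "In patients whom drug was held, ruxolitinib may be restarted at 50% of the MTD".
- After a reduction: "In patients whom drug dose was decreased, ruxolitinib may be increased to the previous dose (MTD").
- Condition for both: "after platelet count has improved to pre-ruxolitinib baseline levels and/or febrile neutropenia has resolved for at least 2 weeks".

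The next sentence is the one at issue. Its trigger is "If criteria is met for discontinuation/dose modification" and its consequence is "then ruxolitinib must be discontinued with no potential for restart". The sentence after that returns to titration: "The objective for restarting or escalating after a reduction for safety is to find the highest safe dose", with increases generally of no more than 5 mg BID and no more often than every 2 weeks.

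Section 10.3, on hepatic impairment, requires a hold and allows a restart at 50% of the MTD. It discontinues the drug only if the impairment occurs a second time in the same patient.

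**The concern.** The no-restart sentence is mandatory and has no wording such as again, a second time or after restart. A platelet-driven reduction is a dose modification in the ordinary sense. Taken at its word, the sentence ends treatment at the event for which the preceding sentence permits a return to full dose. The re-escalation rule would then have no patients to apply to.

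A site that follows the mandatory sentence would permanently stop the drug in a patient whom the adjacent text allows to continue at a lower dose. A site that follows the restart rules would not. External sites take part (Sections 11 and 17.7), so the two could diverge. The triggers are foreseeable: patients may enter with platelets as low as 35,000/µL (Section 4.2.1.1), and blood counts are taken weekly for the first 16 weeks (Section 13.2.1).

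A patient stopped before completing 8 weeks of therapy also leaves the evaluable-patient analysis in Section 15.5, though not the main analysis of all treated patients.

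**Working it through.** **1. Which events the sentence catches.** The plan states no figure on this point, so the first check sets the text side by side.

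| Event | Rule around the sentence | The sentence read literally |
|---|---|---|
| First mandatory platelet reduction | May return to the MTD on recovery | Terminal: plainly a dose modification |
| First platelet or bleeding hold, or febrile-neutropenia halt | May restart at 50% of the MTD on recovery | Terminal only if discontinuation means the hold/halt criteria |
| CYP3A4-inhibitor reduction | Own rule: resume the prior BID dose after the inhibitor course | Taken as governed by its own rule |
| Hepatic hold | Own rule in 10.3: terminal on second occurrence | Taken as governed by its own rule |

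The second row is less certain than the first. The Section 10 heading separates delays from modifications, temporary stops are called held, halted or interrupted, and Section 9.3 has its own list of reasons for which study drug must be discontinued. Against that, 10.2 defines no separate discontinuation criteria. No other section supplies a recurrence qualifier for 10.2.

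**2. What the literal reading costs one patient.** Inputs: 20 mg BID, i.e. 40 mg/day (synopsis, Treatment plan); 16 weeks of treatment (Section 7), i.e. 16 × 7 = 112 days; reduced doses of 75% of the MTD = 30 mg/day and 50% of the MTD = 20 mg/day (Section 10.2). The trigger week *w* is illustrative, and the reduced dose is assumed never to be re-escalated or interrupted.

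- Planned dose = 40 × 112 = 4,480 mg.
- Literal sentence = 40 × 7*w*.
- 75% tier = 40 × 7*w* + 30 × 7(16 − *w*).
- 50% tier = 40 × 7*w* + 20 × 7(16 − *w*).

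For *w* = 4: literal = 40 × 28 = 1,120 mg; 75% tier = 1,120 + 30 × 84 = 3,640 mg; 50% tier = 1,120 + 20 × 84 = 2,800 mg.

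| Trigger at end of week | Literal | 75% tier | 50% tier |
|---|---|---|---|
| 2 | 560 mg (12.5%) | 3,500 mg (78.1%) | 2,520 mg (56.3%) |
| 4 | 1,120 mg (25%) | 3,640 mg (81.3%) | 2,800 mg (62.5%) |
| 8 | 2,240 mg (50%) | 3,920 mg (87.5%) | 3,360 mg (75%) |
| 12 | 3,360 mg (75%) | 4,200 mg (93.8%) | 3,920 mg (87.5%) |

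**3. Whether the design figures move.** Section 15.2 gives a null rate of 10%, an alternative of 30%, and boundaries of 1/10 and 5/29.

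- Early termination under the null = 0.9^10 + 10 × 0.1 × 0.9^9 = 0.736 (stated 0.74).
- Probability of declaring activity = sum over x = 2 to 10 of P(X₁ = x) × P(X₂ ≥ 6 − x), with 10 patients in stage 1 and 19 in stage 2. This is 0.047 at 10% (stated 0.05) and 0.805 at 30%, so the type II error is 0.195 (stated 0.19).

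These reproduce. They depend only on the boundaries and the two assumed rates, so the dosing sentence does not change them.

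**The case against.** The strongest reply is that context already shows the intent. The sentence stands between the restart rules and the objective of finding the highest safe dose, inside a strategy introduced as recommended. A first-event reading would empty those rules, and 10.3 shows the same pattern with its qualifier written out. The protocol's requirements are reviewed at a compulsory initiation teleconference (Section 17.7). The investigator and study team also review adverse events and the application of dosing rules every two weeks (Section 17.6). Nothing in the documents shows a site applying the literal reading. If one did, the error would be to stop drug early, not to give too much.

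Most of this stands, and it limits the severity. It does not remove the point. The written instruction still says something other than what was probably meant. Even read as a recurrence rule, it leaves open whether a second platelet reduction is terminal or only a second hold. Oversight can catch a misapplication, but it does not settle that question.

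The exposure comparison also has limits. It applies to reductions. A held patient may restart only after the recovery condition is met, and some may never meet it; for them the two readings give the same result.

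A reader might infer that response data would be lost. The documents do not support that as an automatic result: Section 9.3 asks for withdrawal assessments and all scheduled follow-up visits, and Section 13.5 provides an end-of-treatment visit, with CT and marrow at the coordinating investigator's discretion.

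**Conclusion.** The sentence is wrong as written. It makes a first mandatory platelet reduction terminal, and arguably a first hold or febrile-neutropenia halt as well, against the text on either side of it and against Section 10. Recurrence is the probable meaning.

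The demonstrable consequence is at patient level: avoidable permanent loss of drug. For a week-4 reduction, the patient receives 25% of the planned 16-week dose under the literal rule, against 81% or 62.5% if treatment continues at the 75% or 50% tier. That rests on an illustrative trigger week and on no later change of dose.

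Two stronger conclusions are tempting and not supported. The first is that the trial loses a predictable number of patients or a known amount of power. The documents give no rate of these events in CMML. The myelofibrosis dose-change counts in Section 2.3 cover reductions and interruptions for any cause in another disease, so they do not match the 10.2 triggers, and the Simon figures are unaffected. The second is that every hold or halt is certainly terminal; that depends on reading discontinuation as the hold/halt criteria rather than Section 9.3.

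Severity is minor to should-fix. Confidence in the textual contradiction is high.

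**What to change.** Replace the sentence in Section 10.2 with:

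*If criteria for a hold (Section 10 or 10.2) are met again after ruxolitinib has been restarted, ruxolitinib must be permanently discontinued; a first hold or a dose reduction does not by itself require discontinuation.*

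The sponsor should add a repeat platelet reduction to the terminal criteria only if that is intended. A terminal second reduction would fit poorly with titrating each patient to the highest safe dose in steps of 5 mg BID.

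The cost is a one-sentence amendment, one sponsor decision and notification of the sites. No procedures, patients or analyses are added.
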